6.1.3 Relationship to Study Drug

For the assessment of drug event relationship, LCIG should be considered a therapeutic system consisting of drug, devices and placement procedure. Causality assessments are always made over the system as a whole.

For the assessment of drug event relationship, those randomized to OMT should evaluate relatedness to any of the subject's anti-PD medication.

The Investigator will use the following definitions to assess the relationship of the adverse event to the use of study drug:

Reasonable Possibility	After consideration of factors including timing of the event, biologic plausibility, clinical judgment, and potential alternative causes, there is sufficient evidence (information) to suggest a causal relationship.
No Reasonable Possibility	After consideration of factors including timing of the event, biologic plausibility, clinical judgment, and potential alternative causes, there is insufficient evidence (information) to suggest a causal relationship.

For causality assessments, events assessed as having a reasonable possibility of being related to the study drug will be considered "associated." Events assessed as having no reasonable possibility of being related to study drug will be considered "not associated." In addition, if the Investigator has not reported causality or deemed it not assessable, AbbVie will consider the event associated.

[figure not shown]
If an Investigator's opinion of no reasonable possibility of being related to study drug is given, an Other cause of event must be provided by the Investigator for the serious adverse event.

6.1.4 Adverse Event Collection Period

Protocol-related nonserious adverse events that occur after signing the informed consent, prior to the start of study drug administration, will be collected. All adverse events reported from the time of randomization until 30 days following last OMT dose, last study visit, discontinuation of study drug administration, removal of the PEG-J tube or Last LCIG Commercial Transition Visit have elapsed will be collected, whether solicited or spontaneously reported by the subject. In addition, serious adverse events and protocol related non serious adverse events will be collected from the time the subject signed the study-specific informed consent.

Adverse event information will be collected as shown in [Figure 3](#).

Figure 3. Adverse Event Collection

6.1.6 Pregnancy

Pregnancy in a study subject must be reported to AbbVie within 1 working day of the site becoming aware of the pregnancy. Subjects who become pregnant during the study must be discontinued (Section 5.4.1).

Information regarding a pregnancy occurrence in a study subject and the outcome of the pregnancy will be collected.

Pregnancy in a study subject is not considered an adverse event. The medical outcome for either mother or infant, meeting any serious criteria including an elective or spontaneous abortion, is considered a serious adverse event and must be reported to AbbVie within 24 hours of the site becoming aware of the event.

6.2 Product Complaint

6.2.1 Definition

A Product Complaint is any Complaint (see Section 6.0 for the definition) related to the biologic or drug component of the product or to the medical device component(s).

For a product this may include, but is not limited to, damaged/broken product or packaging, product appearance whose color/markings do not match the labeling, labeling discrepancies/inadequacies in the labeling/instructions (example: printing illegible), missing components/product, device not working properly, or packaging issues.

For medical devices, a product complaint also includes all deaths of a patient using the device, any illness, injury, or adverse event in the proximity of the device, an adverse

event that could be a result of using the device, any event needing medical or surgical intervention including hospitalization while using the device and use errors.

Any information available to help in the determination of causality by the device to the events outlined directly above should be captured.

6.2.2 Reporting

Product Complaints concerning the investigational product and/or device must be reported to the Sponsor within 24 hours of the study site's knowledge of the event via the eCRF or Product Complaint form if eCRF is unavailable. Product Complaints occurring during the study will be followed-up to a satisfactory conclusion. All follow-up information is to be reported to the Sponsor (or an authorized representative) and documented in source as required by the Sponsor. Product Complaints associated with adverse events will be reported in the study summary. All other complaints will be monitored on an ongoing basis.

Product Complaints may require return of the product with the alleged complaint condition (cassette, pump, tubing, etc.). In instances where a return is requested, every effort should be made by the investigator to return the product within 30 days. If returns cannot be accommodated within 30 days, the site will need to provide justification and an estimated date of return.

The description of the complaint is important for AbbVie in order to enable AbbVie to investigate and determine if any corrective actions are required.

8.0 Statistical Methods and Determination of Sample Size

8.1 Statistical and Analytical Plans

8.1.1 Analysis Datasets

Intent-to-Treat Dataset

Unless specified otherwise, the efficacy analyses will be performed on the intent-to-treat dataset which will include all subjects who are randomized to the optimized medical treatment, and all subjects who are randomized to LCIG and received at least one dose of study drug. For assessments of efficacy, the treatment period will begin the day after randomization for subjects randomized to optimized medical treatment, and the day of first LCIG infusion following PEG-J placement for subjects randomized to LCIG

treatment. The treatment period will end on the day of the final visit for subjects randomized to OMT, and on the last day of LCIG study drug infusion for subjects randomized to LCIG treatment.

The last assessment prior to randomization will be considered baseline and the last assessment that is no more than 2 days after the end of the treatment period will be considered the final evaluation.

Safety Dataset

The safety analyses will be performed on the safety dataset which will include all subjects who are randomized to the optimized medical treatment, and all subjects who are randomized to LCIG and have study device (NJ and/or PEG-J) placement. For assessments of safety, the treatment period will begin the day after randomization for subjects randomized to optimized medical treatment, and the day of NJ placement (or PEG-J placement if no NJ) for subjects randomized to LCIG. The treatment period will end on the day of the final visit for subjects randomized to optimized treatment, and on the last day of LCIG infusion or device removal (whichever is later) in the study for subjects randomized to LCIG. The last assessment prior to randomization will be considered baseline and the last assessment that is no more than 2 days after the end of the treatment period will be considered the final evaluation.

8.1.2 Demographic, Other Baseline Characteristics, Subject Disposition, and Concomitant Medication

Demographic and Other Baseline Characteristics

All demographic variables will be summarized for the safety dataset unless otherwise specified.

For continuous demographic variables, including age, weight, height and body mass index (BMI), descriptive statistics (number of subjects with non-missing data, mean, standard deviation, median, minimum, and maximum) will be provided for each treatment group,

and for both treatment groups combined. Overall treatment group differences will be tested using one-way ANOVA.

For categorical demographic variables, including gender and race, the number and percentage of subjects in each category will be provided for each treatment group, and for all treatment groups combined. Overall treatment group comparability will be tested using Fisher's exact test.

For the ITT data set, baseline NMSS total score and PDSS-2 total score will be summarized. One-way ANOVA will be used to assess the comparability of treatment groups.

Medical History

Medical history data will be summarized for the safety dataset using body systems and conditions/diagnoses as captured on the eCRF. Parkinson's disease history will also be summarized.

Subject Disposition

The number and percentage of subjects contributed by each country and site will be summarized for each treatment group and for all treatment groups combined for the safety dataset.

The number and percentage of subjects who prematurely discontinue study will be summarized by treatment group and overall for the safety dataset for the primary reason as well as for all reasons collected. In the summary, the number and percentage of subjects who discontinue due to any reason as well as due to each specific primary reason will be presented. Subjects may report multiple reasons for prematurely discontinuing study, but the primary reason for discontinuation will be indicated in the eCRF and used to infer treatment group difference in subject's disposition. The treatment group differences in the percentage of subjects who discontinued for any reason as well as for each specific reason will be assessed using Fisher's exact test.

Previous and Concomitant Medications

Previous and concomitant medications will be coded by the most recent World Health Organization (WHO) Drug dictionary. Previous and concomitant medications will be summarized by treatment group for the safety dataset. No statistical testing will be performed.

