The Study Termination eCRF must be completed for all subjects who have entered the study (i.e., have signed the Informed Consent). Subjects dropping out prior to randomization will be considered Screen Failures and the reason for Screen Failure will be entered in the eCRF. In case of Premature Discontinuation of the subject after randomization, the primary reason for Premature Discontinuation will be entered in the eCRF.

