5.0 Analysis Populations

Analyses will be performed utilizing the following datasets.

Intent-to-Treat Dataset

The intent-to-treat dataset will include all subjects who are randomized to the optimized medical treatment, and all subjects who are randomized to LCIG and received at least one dose of study drug. The intent-to-treat dataset will be used to summarize efficacy and health outcome measures.

Safety Dataset

The safety dataset will include all subjects who are randomized to the optimized medical treatment, and all subjects who are randomized to LCIG and have study device (NJ and/or PEG-J) placement. The safety dataset will be used to summarize safety data during the OMT and LCIG treatment period.

All Randomized Dataset

The all randomized dataset will include all subjects who are randomized to the optimized medical treatment, and all subjects who are randomized to LCIG treatment. The all randomized dataset will be used to perform sensitivity analysis.

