7.0 Subject Disposition, Baseline Characteristics and Concomitant Medications

7.1 Subject Disposition

An overall summary of the disposition of all screened subjects will be prepared. The total number of subjects in each of the following categories as well as the number at each site will be presented:

- Screened, screen failed;
- Randomized to OMT group, prematurely discontinued treatment from OMT group, completed the planned 26 weeks of treatment in OMT group, continued to Extension Period, prematurely discontinued during the Extension Period, completed the Extension Period; Randomized to LCIG group, no NJ/PEG-J placed, NJ placed, prematurely discontinued during NJ, PEG-J placed, prematurely discontinued treatment during PEG-J, completed the planned 26 weeks of treatment in LCIG group, continued to Extension Period, prematurely discontinued during the Extension Period, completed the Extension Period.

An additional summary of screen failures will be prepared with the number and percentage of screened subjects who screen failed overall and for each specific screen failure reason.

Additional summaries of premature study drug discontinuations during the 26-week Treatment Period for both treatment groups, and during the Extension/Transition Period, will be prepared for the Safety Dataset with the number and percentage of subjects who prematurely discontinued for any reason, for each specific primary reason, and for each specific reason.

A listing will be prepared of all randomized subjects who are not included in the primary efficacy analysis. The listing will include each subject number and reason for exclusion.

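### Discontinuation is compared on a dataset that keeps every OMT subject but only LCIG subjects with a tube placed, so any LCIG withdrawal before placement is left out of the compared rate

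*Protocol*

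**What the plan says.** Protocol 8.1.2 (Subject Disposition) sets the population: "The number and percentage of subjects who prematurely discontinue study will be summarized by treatment group and overall for the safety dataset". The primary reason is to serve for inference about a difference between the arms. The difference for any reason and "for each specific reason will be assessed using Fisher's exact test".

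Protocol 8.1.1 describes "the safety dataset which will include all subjects who are randomized to the optimized medical treatment". For the other arm, SAP 5.0 agrees with Protocol 8.1.1 and admits "all subjects who are randomized to LCIG and have study device (NJ and/or PEG-J) placement".

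SAP 7.1 stays with this population. It calls for "Additional summaries of premature study drug discontinuations during the 26-week Treatment Period for both treatment groups", and these "will be prepared for the Safety Dataset with the number and percentage of subjects who prematurely discontinued for any reason", as well as by primary reason and by each reason.

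Four other provisions bear on the point:

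- SAP 7.1 opens with a disposition table of all screened subjects, in total and by site. For OMT it gives the numbers randomized, discontinued and completed. For LCIG it gives the numbers randomized, with neither tube placed, with an NJ tube placed, discontinued in the NJ phase, with a PEG-J placed, discontinued after that, and completed.
- SAP 7.1 also requires a listing of randomized subjects left out of the primary efficacy analysis, with the reason for exclusion.
- SAP 5.0 defines an All Randomized Dataset and assigns it to sensitivity analysis.
- Protocol 5.4.1 secures the data: "In case of Premature Discontinuation of the subject after randomization, the primary reason for Premature Discontinuation will be entered in the eCRF".

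**The concern.** To enter the safety dataset an OMT subject need do nothing after randomization. An LCIG subject must get as far as tube placement. Between those two events lies a window that only the LCIG arm has. Protocol 5.1.2.2 and 5.2.3.2 allow up to 14 days after randomization to taper the other anti-PD drugs, and the notes to Protocol Table 3 stop placement if the V3 PT/PTT is abnormal. OMT subjects are counted from the day after randomization (Protocol 5.1.2.1).

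An LCIG subject who leaves in that window, for instance because the taper is not tolerated or the tube is declined, vanishes from the LCIG rate altogether. The Fisher test then sets one complete randomized group against a part of the other, chosen by an event after randomization. The reasons most particular to starting LCIG would be missing from the by-reason table, and from one arm only.

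**Working it through.** **Is there a figure in the plan to reproduce?** Not for discontinuation: neither document states or predicts a rate. The only related figures are in Protocol 8.2. Simulating that section's assumptions (differences of 16.6 and 8.8 points, SDs 24 and 12.2, correlation 0.5, Hochberg at two-sided 0.05) gives power of 90.3% with 37 per group. With 44 per group and 10% carried forward from baseline it gives 90.5%. The plan states 90% for both. The sample size is therefore sound on its own inputs, and nothing below depends on it.

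**Inputs**

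- 88 subjects randomized 1:1, so 44 per arm (Protocol 8.2).
- x = LCIG subjects who withdraw before any tube is placed. Not given in the documents; assumed.
- y = LCIG subjects who withdraw later, including in the NJ phase. Not given; assumed.
- OMT withdrawals: assumed 4 of 44 = 9.1%, the same under either dataset.

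**Formulas**

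- LCIG rate as planned (safety dataset): y/(44-x).
- LCIG rate on all randomized: (x+y)/44.
- Shortfall: (x+y)/44 - y/(44-x) = x(44-x-y) / [44(44-x)].

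The shortfall is zero when x = 0. It is positive whenever x > 0 and at least one LCIG subject does not withdraw. The direction is thus fixed by algebra; only the size depends on the counts.

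**Numbers.** For x = 4, y = 4 the shortfall is 4 × 36 / (44 × 40) = 144/1760 = 8.2 points. Over a range, with two-sided Fisher P values against OMT 4/44:

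| x | y | As planned | All randomized | Shortfall (points) | P as planned | P all randomized |
|---|---|---|---|---|---|---|
| 0 | 4 | 4/44 = 9.1% | 4/44 = 9.1% | 0 | 1.00 | 1.00 |
| 1 | 4 | 4/43 = 9.3% | 5/44 = 11.4% | 2.1 | 1.00 | 1.00 |
| 2 | 4 | 4/42 = 9.5% | 6/44 = 13.6% | 4.1 | 1.00 | 0.74 |
| 4 | 4 | 4/40 = 10.0% | 8/44 = 18.2% | 8.2 | 1.00 | 0.35 |
| 6 | 4 | 4/38 = 10.5% | 10/44 = 22.7% | 12.2 | 1.00 | 0.14 |
| 8 | 4 | 4/36 = 11.1% | 12/44 = 27.3% | 16.2 | 1.00 | 0.051 |
| 7 | 6 | 6/37 = 16.2% | 13/44 = 29.5% | 13.3 | 0.50 | 0.029 |

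Each withdrawal before placement costs about 2 points. For x from 2 to 6 with y = 4, the LCIG minus OMT gap is 0.4 to 1.4 points as planned and 4.5 to 13.6 points on all randomized subjects.

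**The case against.** The strongest reply is that SAP 7.1 already shows these subjects. Its table of all screened subjects gives the randomized denominator for both arms and splits LCIG by stage. The listing of exclusions also names anyone without a tube, since such a subject has no LCIG dose and is outside the intent-to-treat set. Adverse events between randomization and placement are summarized separately (Protocol 8.1.4.2, SAP 10.2.1). This stands: a reader who infers that early withdrawals are concealed would be wrong, and the any-reason rate can be rebuilt by hand. Neither output supplies a percentage, a breakdown by discontinuation reason, or a comparison between arms on that denominator.

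A second reply is that SAP 7.1 speaks of discontinuing study drug, and a subject who never received LCIG cannot discontinue it. SAP 5.0 says of the dataset: "The safety dataset will be used to summarize safety data during the OMT and LCIG treatment period". For study drug discontinuation that is defensible. Protocol 8.1.2, however, speaks of discontinuing the study, and the restriction has no counterpart in the OMT arm. SAP 7.1 does not repeat the Fisher test, but SAP 12.0 declares no change in analysis from Protocol Amendment 4, so the test remains planned.

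Three further limits are fair:

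- The 10% in Protocol 8.2 might be read as a forecast of withdrawals before placement. It is not: it means no efficacy assessment after randomization, in either arm, from any cause.
- The PT/PTT rule stops placement and refers the case to the medical monitor. It does not say that the subject leaves the study.
- Discontinuation is not among the safety and tolerability measures listed in Protocol 4.0 and 5.3.4, so it cannot be called a named tolerability endpoint.

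**Conclusion.** The point holds as a conditional one. If at least one LCIG subject withdraws between randomization and tube placement, the compared LCIG discontinuation rate is too low, by about 2 points per such subject at 44 per arm, and the comparison is no longer between the groups as randomized. The example of 10.0% instead of 18.2% rests on assumed counts (x = 4, y = 4). In that example neither P value is significant (1.00 and 0.35), and only more lopsided assumptions, such as x = 7 and y = 6, carry the test across 0.05.

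A reader might infer that LCIG dropout will certainly be understated. The documents do not support that: they give no count of withdrawals before placement, and with none the two rates are identical. Subjects who leave during the NJ phase are already included. The disposition tests enter no success rule, so neither the primary analysis nor the sample size is touched.

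**What to change.** In Protocol 8.1.2 and SAP 7.1, produce the 26-week discontinuation summary (any reason, primary reason, each reason) and the Fisher tests on the All Randomized Dataset, and widen that dataset's stated use in SAP 5.0 to cover this. Show withdrawals before placement as a separate LCIG row. Keep the safety-dataset summary of study drug discontinuation as supportive, labelled as such.

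The cost is a few lines of wording and one changed denominator. No new data are needed, because the primary reason is recorded for every premature discontinuation after randomization. The downside for the sponsor is that the LCIG dropout rate may look less favourable.

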8.1.3 Efficacy Analysis

All efficacy analyses will be performed on the ITT dataset unless otherwise specified. Comparisons between OMT and LCIG groups will be performed with two-sided tests at the significance level of 0.050.

Unless otherwise specified, the "baseline" for efficacy variables is defined as the last assessment taken on or before the day of randomization, and the "final observation" refers to the last non-missing observation in the Treatment Period (including evaluations conducted within 2 days after the last dose of study drug for subjects randomized to LCIG).

8.1.3.1 Primary Efficacy Analysis

There are 2 alternative primary efficacy variables, change from baseline to Week 26 for NMSS total score and change from baseline to Week 26 for PDSS-2 total score. Either variable considered statistically significant after multiplicity adjustment is sufficient to declare success of the study.

NMSS Total Score

The NMSS was developed to assess non-motor symptoms in PD. It is obtained through interview and rated by health professionals. It contains 30 questions grouped into 9 domains: cardiovascular (2 items), sleep/fatigue (4 items), mood/cognition (6 items), perceptual problems/hallucinations (3 items), attention/memory (3 items), gastrointestinal tract (3 items), urinary (3 items), sexual function (2 items), and miscellaneous (4 items). Each question is scored with respect to severity and frequency. Severity is rated on a

scale where 0 = none, 1 = mild, 2 = moderate and 3 = severe. Frequency is rated on a scale where 1 = rarely, 2 = often, 3 = frequent and 4 = very frequent. Item scores are calculated as the product of severity and frequency. Domain scores and a total score are obtained by summing the item scores.

PDSS-2 Total Score

The PDSS-2 was developed from the PDSS based upon the need for a treatment-measuring tool containing PD-specific sleep disorders. The instrument was extended to address specific sleep disturbances such as RLS, akinesia, pain, and sleep apnea. The frequency is assessed for the 15 sleep problems based on a 5-point Likert-type scale (ranging from 0 [never] to 4 [very often]). Scores are calculated for each domain as well as a total score.

Primary Analysis Model and Multiplicity Adjustment

The primary efficacy analysis model is a likelihood-based mixed-effects model repeated measures (MMRM) analysis of the change from baseline for each post-baseline observation using all observed data. The model will include fixed, categorical effects for treatment, country, visit, and treatment-by-visit interaction, with continuous fixed covariates for baseline score and the baseline score-by-visit interaction. The primary comparison will be the contrast between LCIG and optimized oral treatment at the Week 26 Visit.

The two-sided P values obtained from the MMRM model for NMSS total score change from baseline to Week 26 and PDSS-2 total score change from baseline to Week 26 will be adjusted for multiplicity using the Hochberg procedure. This method controls the family-wise error rate (FWER) at a pre-specified significance level ($\alpha = 0.05$). Specifically, the following steps will be followed:

- If the larger of the 2 P values is ≤ 0.05 (i.e., both P values are ≤ 0.05), both endpoints are considered statistically significant.

- If the larger of the 2 P value is > 0.05 , then compare the smaller P value with 0.025. The second endpoint is statistically significant if the P value is ≤ 0.025 ; otherwise, neither endpoint is considered statistically significant.

